10.3.3 Pharmacokinetic Analyses

Endpoint	Statistical Analysis Methods
BMS-986205 Cmax, AUCtau, CLT/F, Vss/F	Summary statistics: geometric means and coefficients of variation
BMS-986205 T-HALF(eff, AUC)	Summary statistics: means and SD
BMS-986205 Tmax	Summary statistics: medians and ranges
BMS-986205 Ctrough	Summary statistics to assess attainment of steady state: geometric means and coefficients of variation; plots vs time by dose
BMS-986205 %UR	List will be presented for %UR. Plots of individual cumulative percent of dose recovered in urine versus end of interval time. Mean plots of cumulative percent of dose recovered in urine versus end of interval time
[REDACTED]	
Nivolumab end of infusion (Ceoi), Ctrough	Summary statistics

[figure not shown]

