### **5 SAMPLE SIZE AND POWER**

The sample size for this study is not based on statistical power, but based on consideration of the precision of the estimate of geometric means of Cmax and AUC of BMS-986205. Based on preliminary PK results from Study CA017003 cohorts 25 mg to 200 mg, assuming the inter-subject CV for AUC24 is 42%, a sample size of 12 PK evaluable subjects will be sufficient for the point estimates of the mean PK parameter to fall within 80% to 125% of the true value, with 91% confidence level. Assuming the inter-subject CV for Cmax is 29%, a sample size of 12 PK evaluable subjects will be sufficient for the point estimates of the mean PK parameter to fall within 80% to 125% of the true value, with 98% confidence level. Twelve subjects will provide 90% probability of observing at least one occurrence of a specific AE that would occur with an 18% incidence in the population.

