### **7.7.1      *Pharmacokinetic Concentrations***

Analyses for this section will be provided by the CPAR group. Summary statistics and listings will be provided for the following pharmacokinetic concentrations by treatment, cycle, study day and time on the BMS-986205 and nivolumab PK Subjects.

- Plasma concentrations of BMS-986205 and select metabolites
- Serum concentrations of nivolumab

Plots of the individual and mean concentration profile vs. time by cycle/study day for BMS-986205 and select metabolites will be provided.

A by-subject listing of BMS-986205/select metabolites plasma and nivolumab serum concentrations will be provided.

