### **7.7.2      *Pharmacokinetic Parameters***

Summary statistics will be provided for all individual PK parameters by treatment, cycle, study day and time where data is available. Geometric means and coefficients of variation will be presented for the selected following PK parameters for BMS-986205 or corresponding metabolites: Cmax, AUC(TAU), CLT/F, Ctrough, AI, %UR24, MR\_AUC(TAU) and MR\_Cmax. Mean and standard deviation will be presented for T-HALF(T-HALFeff\_AUC). Median, minimum, and maximum will be presented for Tmax. Drug accumulation indices (AI) is defined as the ratio of AUC(TAU) and Cmax at steady state to after the first dose. Effective T-Half, which will be calculated only if AI > 1, is defined as following:

$$\text{Effective T - Half} = \frac{\text{dosing interval} * \log(2)}{\log\left(\frac{AI}{AI - 1}\right)}$$

Plot of geometric mean with 90% CI of Ctrough vs. study day and cycle will be presented to assess if steady state is reached.

Summary statistics will be provided for the following PK parameters for nivolumab: Ctrough, Ceoi.

A by-subject listing of BMS-986205/select metabolites and nivolumab PK parameters will be provided.

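### Steady state is to be judged from per-day mean troughs and between-participant 90% CIs, although a paired trough ratio from the same Cycle 0 samples would estimate the change directly

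*SAP*

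**What the plan says.** SAP 7.7.2: "Plot of geometric mean with 90% CI of Ctrough vs. study day and cycle will be presented to assess if steady state is reached". Protocol 10.3.3, in the row for Ctrough, plans "Summary statistics to assess attainment of steady state: geometric means and coefficients of variation; plots vs time by dose". Neither section names a reference day, a within-participant contrast, a margin, or a rule for deciding from the plot.

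Other displays exist. SAP 7.7.1 adds: "Plots of the individual and mean concentration profile vs. time by cycle/study day for BMS-986205 and select metabolites will be provided". By-subject listings of concentrations and of PK parameters are also planned (SAP 7.7.1 and 7.7.2).

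The steady-state judgement feeds two reported parameters. SAP 7.7.2 defines the accumulation index (AI) as the "ratio of AUC(TAU) and Cmax at steady state to after the first dose" and computes effective half-life from AI.

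Protocol Table 9.5.2-1 schedules BMS-986205 predose samples on C0D2, C0D8 and C0D14. A further sample follows 24 hours after the C0D14 dose, labelled C0D15 or C1D1 predose depending on when Cycle 1 starts. Later predose samples fall on C1D2, C3D1 and every fourth cycle from C5D1.

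**The concern.** Whether steady state has been reached is a question about change: has a participant's trough stopped rising from one day to the next? A separate 90% CI for each day's geometric mean answers another question, namely where the average level lies. Its width comes from the full between-participant spread. That spread largely cancels when the same participant is compared with himself or herself, and the Cycle 0 schedule supplies exactly those pairs. The plot is therefore an inefficient basis for judging change. The individual plots and listings show the pairs but do not summarise them.

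What depends on it is the reading of AI and effective half-life. Full profiles after repeated dosing are taken only on C0D14 and C1D1, so both parameters assume a plateau by about Day 14. If trough is still rising then, both are understated, and no planned output measures that.

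Across cycles there is a second problem. The plotted means come from whoever is still on treatment, and the SAP does not restrict comparisons to participants who contribute both time points. Change in trough is then mixed with change in who remains.

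**Working it through.** **Inputs from the documents.** n = 12 ("a sample size of 12 PK evaluable subjects will be sufficient", SAP Section 5). The same section gives two CVs: "assuming the inter-subject CV for AUC24 is 42" per cent and "Assuming the inter-subject CV for Cmax is 29" per cent. Neither is for Ctrough.

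**Inputs assumed.** The Ctrough CV (29%, 42% and 60% tried) and the correlation of a participant's log troughs between days (0.6 to 0.9). The true rise of 25% is a chosen illustration. So is the rule that overlapping 90% CIs count as a plateau.

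**Step 1: the plan's own figures.** With s = √ln(1 + CV²), the chance that the geometric mean falls "within 80% to 125% of the true value" is 2F(ln 1.25 / (s/√12)) − 1, where F is Student t with 11 df.
- AUC24: s = 0.403, argument 0.223/0.116 = 1.92, result 91.9% (stated 91%).
- Cmax: s = 0.284, argument 0.223/0.082 = 2.72, result 98.0% (stated 98%).

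Both reproduce closely. The documents give no figure for the steady-state check itself.

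**Step 2: interval widths.** The per-day 90% CI half-width on the log scale is 1.796 × s/√12. For two adjacent intervals of typical width to separate, the means must differ by twice that.
- CV 29%: half-width 0.147 (factor 1.16); separation needs a ratio of about exp(0.295) = 1.34.
- CV 42%: 0.209 (factor 1.23); separation needs about exp(0.418) = 1.52.
- CV 60%: 0.287 (factor 1.33); separation needs about exp(0.575) = 1.78.

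The paired half-width is 1.796 × s√(2(1 − ρ))/√12. At CV 42% and ρ = 0.8 it is 1.796 × 0.255/3.464 = 0.132, a factor of 1.14 against 1.23 per day.

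**Step 3: simulation of a true 25% rise.** Paired lognormal troughs on two days, n = 12, 200,000 replicates per setting. Each cell gives results for ρ = 0.6 / 0.8 / 0.9.

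| Trough CV | Per-day 90% CIs overlap | Paired 90% CI excludes 1 | Observed mean ratio above 1.10 |
|---|---|---|---|
| 29% | 76.4 / 80.0 / 82.4% | 88.5 / 99.1 / 100% | 95.9 / 99.3 / 100% |
| 42% | 92.9 / 96.0 / 97.5% | 64.2 / 88.4 / 99.1% | 89.0 / 95.9 / 99.3% |
| 60% | 97.6 / 99.1 / 99.6% | 42.9 / 66.5 / 89.8% | 81.4 / 89.7 / 96.2% |

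Overlap becomes more frequent as ρ rises: the observed ratio settles nearer 1.25, well below what separation needs, and the per-day intervals do not narrow. The paired interval does narrow. At ρ = 0 the overlap figures are 70.0%, 85.5% and 92.0% for the three CVs.

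**Step 4: effect on AI and half-life.** Assume linear one-compartment accumulation with daily dosing, where r is the fraction remaining after 24 hours. Predose C0D8 follows 7 doses and predose C0D14 follows 13, so the trough ratio is (1 − r¹³)/(1 − r⁷). A ratio of 1.25 gives r = 0.829, a half-life of about 3.7 days.
- True AI: 1/(1 − r) = 5.9.
- AI observed on Day 14: (1 − r¹⁴)/(1 − r) = 5.4, about 7% low.
- Effective half-life from the SAP formula: about 3.4 days against 3.7, about 8% low.

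A 50% rise from C0D8 to C0D14 would leave AI about 32% low. The overlap rule would then miss it in about 50% of trials at CV 42% and 81-88% at CV 60%.

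**The case against.** The strongest reply is that the SAP contains no overlap rule. It says the plot is presented to assess steady state, and an experienced reader would follow the sequence of means, the individual profiles and the listings as well as the intervals. At CV 42% and correlation 0.6 to 0.9, a true 25% rise gives an observed mean ratio above 1.10 in 89-99% of trials, so it would usually be visible. This stands: the overlap percentages describe one possible misreading, not the plan.

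It does not remove the need for a paired estimate. A visible ratio of 1.10 can also arise by chance when trough is flat. At CV 42% the standard error of the mean log difference is 0.403 × √(2(1 − ρ)/12), which is 0.104, 0.074 and 0.052 for ρ = 0.6, 0.8 and 0.9. Since ln 1.10 = 0.095, a flat trough exceeds 1.10 in about 18%, 10% and 3% of trials. Only an interval for the change itself tells a reader which case applies, and none is planned.

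The second reply is that the consequence is modest. Step 4 supports this for a 25% rise: about 7-8% low, small beside 12 participants and a 42% CV for AUC24. No decision rule in either document depends on a steady-state verdict.

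The third reply concerns a strict remedy. If steady state were accepted only when the paired 90% CI lay inside 80-125%, a truly flat trough would pass in 31%, 77% and 98% of trials at CV 42% (correlation 0.6, 0.8, 0.9), and in 5%, 35% and 80% at CV 60%. SAP Section 5 uses that range for the precision of a mean, not for steady state. This also stands, and it is why the ratio should be reported as an estimate.

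**Conclusion.** The point holds as one of efficiency and pre-specification. The planned means, CVs and per-day intervals do not use the pairing in the Cycle 0 troughs, and no planned output quantifies within-participant change, although AI and effective half-life assume a plateau.

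The size is conditional. With 12 participants, a true 25% rise and correlation 0.6 to 0.9, reading overlap as a plateau would miss the rise in about 76-82% of trials at a trough CV of 29%, 93-97.5% at 42% and 98-99.6% at 60%. At CV 42% the paired 90% CI excludes 1 in 64-99%. The trough CV and the correlation are assumptions.

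A reader might infer something stronger: that the SAP treats overlapping intervals as proof of a plateau, that the plot is the only evidence, or that a 25% rise will be missed more than nine times in ten. The documents support none of these. They state no overlap rule, they plan individual plots and listings, and at the lower of the two CVs they quote (29%) the miss rate is below nine in ten even under that rule. Nor do they support a large bias: under a simple one-compartment model a 25% rise from C0D8 to C0D14 leaves AI about 7% low.

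**What to change.** In SAP 7.7.2:
- Keep the trough plot and label it descriptive.
- Add within-participant geometric mean ratios of Ctrough with 90% CIs for C0D14/C0D8 and for C0D15 (or C1D1 predose)/C0D8, in participants with both samples.
- Limit any trough comparison across cycles to participants who contribute both time points.
- Report the ratios as estimates, with no compulsory 80-125% pass/fail rule.
- State that AI and effective half-life will be described as possibly understated if the ratio and its interval indicate that trough is still rising.

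The cost is a few lines of SAP text and one small table from samples already scheduled. The drawback is that with 12 participants the interval may be inconclusive, and the report should then say so.

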### **7.7.3      *PK Analysis of Urinary recovery data***

Urinary recovery data of BMS-986205/select metabolites will be listed if available.

## 7.8 Pharmacodynamics

Summary statistics of change from baseline for serum kynurenine and tryptophan and corresponding percent change from baseline (C1D1) will be summarized by timepoint.

Line graphs summarizing the mean of absolute and relative (change from baseline and percent change from baseline) values by timepoint will be produced.

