Brain Imaging	X		Brain imaging (CT/MRI) is only required for participants with known history or symptoms of brain metastases and have not had brain imagining within 30 days of anticipated first study drug administration.
Bone Scan	X		As clinically indicated (eg, participants with history of symptoms of bone metastases), but bone scans will not be considered a modality for assessment for measurable disease.

Table 2-2: On-Treatment: BMS-986205 Monotherapy (One 14-Day Cycle) Procedure Outline (CA017076)

Procedure	Cycle 0 D1	Cycle 0 D2	Cycle 0 D8	Cycle 0 D14	Notes
Admit to Clinical Facility	X			X	For the purpose of PK sample collection, participants will be admitted to the clinical facility prior to dosing on C0D1 and C0D14. Participants will remain at the clinical facility until after the dosing on the following day. Participants who are continuing treatment in Cycle 1 after completion of C0D14 will remain at the clinical facility until after dosing on C1D2.
Complete Physical Examination (PE)	X ^a				Predose.
Symptom-Directed PE		X	X	X	Predose.
Vital Signs and Oxygen Saturations	X		X	X	Includes temperature, seated blood pressure, and heart rate. Blood pressure and heart rate should be measured after the subject has been seated quietly for at least 5 minutes.
12-lead ECG	X			X	Collect single ECGs on C0D1 and C0D14 at -1 hour pre-dose and 2 and 4 hours postdose. ECGs should be performed after the subject has been resting supine for at least 5 minutes and should be completed prior to any PK/PD sample blood collections when assessments occur at the same time points.
Laboratory Tests^b					
Chemistry (Excluding LFTs)	X ^a		X	X	Predose: includes assessments for sodium, potassium, chloride, total serum calcium, magnesium, bicarbonate/carbon dioxide, phosphorus, BUN, creatinine, c-reactive protein, glucose, total protein, albumin, amylase, lipase, and LDH.
Methemoglobin	X		X	X	Pre-dose on Day 1, 8 and 14; if elevated, see Section 7.4.6 . Additional samples as clinically indicated.
Reticulocyte counts, haptoglobin and LDH	X		X	X	Reflex when methemoglobin is elevated over ULN. Additional samples as clinically indicated.
CBC with Differential and Platelets	X ^a		X	X	Collect predose. additional samples to be collected as clinically indicated Predose on Day 4 (\pm 1 day).

Table 2-2: On-Treatment: BMS-986205 Monotherapy (One 14-Day Cycle) Procedure Outline (CA017076)

Procedure	Cycle 0 D1	Cycle 0 D2	Cycle 0 D8	Cycle 0 D14	Notes

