Monitor for Serious Adverse Events				X					All SAEs must be collected from the date of subject's written consent until 100 days postdiscontinuation of nivolumab or subject's participation in the study if the last scheduled visit occurs at a later time. SAEs reported in BMS EDC should be approved within 5 business days of entry.
Sample Collection									
PK/ADA Assessments				X					Performed in all subjects. See Section 9.5.2 .
Pharmacodynamic Assessments				X					Performed in all subjects. See Section 9.6 .

Table 2-3: On-Treatment: BMS-986205 + Nivolumab (Multiple 4-Week Cycles) Procedure Outline (CA017076)

Procedure	Cycle 1 (4 weeks)				Cycle 2-12 (4-week cycles)			End of Treatment ^{a,b,c}	Notes
	D1	D8	D15 (±2 days)	D22 (±2 days)	D1	D15 (±2 days)	D22-28		
Efficacy Assessments									
Diagnostic Imaging						X		X	To be collected at the end of Cycle 2 and then every 8 weeks (± 1 week), by methods used at baseline. See Section 9.1 and Section 9.4.2 . Same modality/scanner should be used for all assessments. Assessed by RECIST v1.1; see Appendix 5 . Assessment must be performed prior to initiating the next cycle of treatment.
Brain Imaging					X				As clinically indicated; see Section 9.1 and Section 9.4.2 .
Bone Scan Imaging					X				As clinically indicated; see Section 9.1 and Section 9.4.2 .
Study Drug Administration									
Dispense BMS-986205	X				X				BMS-986205 should be dispensed to participants at Day 1 of each cycle.
BMS-986205 Administration	X				Daily				BMS-986205 administration must be performed daily. BMS-986205 must be administered with a meal at approximately the same time each day. Dosing and associated meal should occur at the site on days when serial PK is collected.
Nivolumab Administration	X				X				Nivolumab should be administered at Day 1 of each cycle.

Table 2-3: On-Treatment: BMS-986205 + Nivolumab (Multiple 4-Week Cycles) Procedure Outline (CA017076)

Procedure	Cycle 1 (4 weeks)				Cycle 2-12 (4-week cycles)			End of Treatment ^{a,b,c}	Notes
	D1	D8	D15 (±2 days)	D22 (±2 days)	D1	D15 (±2 days)	D22-28		
Pill Diary	X			Daily				X	Pill diary should be provided to participants at Day 1 of each cycle. Pill diary must be completed with each administered daily dose of BMS-986205. Review pill diary during each visit for compliance of daily administration of BMS-986205. Collect pill diary at the completion of each cycle and EOT.

^a EOT is defined as the visit where decision is made to discontinue the subject from treatment.

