5 STUDY DESIGN

5.1 Overall Design

This is a Phase 1/2, open-label study of BMS-986205 administered as a monotherapy and in combination with nivolumab in participants with advanced malignant solid tumors.

Treatment will start with a 2-week monotherapy lead-in (Cycle 0) whereby

BMS-986205 100 mg oral daily dose must be administered with a meal at approximately the same time each day.

Participants will then proceed to receive the combination of nivolumab and BMS-986205. Nivolumab will be administered at a dose of 480 mg IV Q4W.

Cycle 0

[figure not shown]
Participants will start with Cycle 0, which is a 2-week BMS-986205 monotherapy lead-in, with a 100-mg oral daily dose. Participants who have received at least 75% of doses in Cycle 0 will be eligible to proceed to receive the combination of nivolumab and BMS-986205 (Cycle 1).

The following AEs will prohibit a participant from proceeding to combination with nivolumab (Cycle 1):

- Grade 2 or higher immune-related AEs (irAEs) considered related to BMS-986205 (eg, immune-mediated pneumonitis, colitis, hepatitis, nephritis, and renal dysfunction) with the exception of immune-mediated hypothyroidism and hyperthyroidism
- Grade 2 AST and ALT elevations that do not resolve to Grade 1 or baseline within 1 week
- \geq Grade 3 elevation of AST, ALT, or total bilirubin that persists for \geq 7 days
- Grade 2 AST or ALT elevation with symptomatic liver inflammation (eg, right upper quadrant tenderness, jaundice, pruritus)
- AST or ALT $> 3\times$ upper limit of normal (ULN) and concurrent total bilirubin $> 2\times$ ULN without initial findings of cholestasis (elevated serum alkaline phosphatase, eg, findings consistent with Hy's law or FDA definition of potential drug-induced liver injury [DILI])
- Grade 2 or greater episcleritis, uveitis, or iritis
- Any other Grade 2 eye pain or blurred vision that does not respond to topical therapy and does not improve to Grade 1 severity within 2 weeks OR requires systemic treatment
- Grade 3 or greater uveitis, pneumonitis, bronchospasm, neurologic toxicity, hypersensitivity reaction, or infusion reaction of any duration requires discontinuation
- Any Grade 3 or greater non-dermatologic, non-hepatic, non-hematologic toxicity with the following specific EXCEPTIONS:

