7.1.2 Nivolumab Administration

During combination therapy, infusion of nivolumab should start approximately 30 minutes following BMS-986205. Nivolumab should be infused over 30 minutes. Further details regarding preparation and administration will be provided separately in site/pharmacy materials. Restrictions related to food and fluid intake are described in [Section 7.7.2](#).

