9.6 Pharmacodynamics

Pharmacodynamic analysis will be performed on serum by measuring kynurenone and tryptophan levels pre and postdose of BMS-986205 and nivolumab [REDACTED]. Serum will be collected at the time points specified in [Table 9.6-1](#).
[REDACTED]

Table 9.6-1: Pharmacodynamic Serum Collection to Measure Kynurenine and Tryptophan Levels Pre- and Postdose of BMS-986205 and Nivolumab

Study Day of Sample Collected	Events	Serum Sample
C1D1	Predose	X
C1D1	Postdose (at 6 hours)	X
C1D2	Predose	X
Disease Progression	--	X

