### **3.2 Secondary**

- To characterize the pharmacodynamic activity of BMS-986205 administered alone and in combination with nivolumab.
- To characterize the immunogenicity of nivolumab when administered in combination with BMS-986205.
- To investigate the preliminary anti-tumor activity of BMS-986205 administered in combination with nivolumab in advanced malignant tumors.

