  - On-treatment evaluations (laboratory tests, pulse oximetry and vital signs) will be defined as evaluations taken after the day (and time, if collected and not missing) of first dose of study treatment. For subjects who are off study treatment, evaluations should be within a safety window of 100 days after the last dose of study treatment if a participant received BMS-986205 + NIVO (or 30 days after the last dose of study treatment if a participant received only BMS-986205).

- Post baseline period by phase:
  - Mono lead-in period starts with the first dose of BMS986205 and end prior to first dose of nivolumab.
    - ◆ Mono lead-in AEs will be defined as AEs with an onset date and time on or after the date and time of the first dose of initial mono study treatment (or with an onset date on or after the day of first dose of initial mono study treatment if time is not collected or is missing) and prior to the date-time of the first dose of nivolumab (or with an onset date prior to the day of first dose of nivolumab if time is not collected or is missing). For subjects who discontinue during Mono lead in, AEs will be included if event occurred within a safety window of 30 days after the last dose of BMS-986205 initial mono study treatment. No “subtracting rule” will be applied when an AE occurs both pre-treatment and post-treatment with the same preferred term and grade.
    - ◆ Mono lead-in evaluations (laboratory tests, pulse oximetry and vital signs) will be defined as evaluations taken after the day and time of the first dose of initial mono study treatment (or with a start date after the day of first dose of initial mono study treatment if time is not collected or is missing) and prior to the date-time of the first dose of nivolumab (or with a start date on or prior to the day of first dose of nivolumab if time is not collected or is missing). For subjects who discontinue during Mono lead in, evaluations will be included if evaluation is taken within a safety window of 30 days after the last dose of BMS-986205 initial mono study treatment.
  - Combination Treatment Period starts with the first dose date-time of initial nivolumab.

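### No kynurenine or tryptophan sample is scheduled before the first BMS-986205 dose, and the PD baseline is C1D1, so activity of BMS-986205 alone cannot be estimated as a change from pre-drug

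*SAP*

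**What the plan says.** The secondary PD objective has two parts (SAP 3.2, matching Protocol Section 4): "To characterize the pharmacodynamic activity of BMS-986205 administered alone and in combination with nivolumab". SAP 4.3.5 makes the endpoint the change and percent change from baseline in serum kynurenine and tryptophan. SAP 7.8 fixes the baseline: "Summary statistics of change from baseline for serum kynurenine and tryptophan and corresponding percent change from baseline (C1D1) will be summarized by timepoint".

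Sampling is set by Protocol Table 9.6-1, titled "Pharmacodynamic Serum Collection to Measure Kynurenine and Tryptophan Levels Pre- and Postdose of BMS-986205 and Nivolumab". It has four rows: C1D1 predose, C1D1 at 6 hours postdose, C1D2 predose and disease progression. In the Schedule of Activities, a PD row appears only in Table 2-3, the combination cycles, with the note "Performed in all subjects. See Section 9.6". Table 2-1 (screening) and Table 2-2 (Cycle 0) have no such row.

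BMS-986205 starts at C0D1, two weeks before C1D1. Protocol 5.1 adds: "Participants who have received at least 75% of doses in Cycle 0 will be eligible to proceed to receive the combination". On C1D1, "infusion of nivolumab should start approximately 30 minutes following BMS-986205" (Protocol 7.1.2). SAP 6.1 draws the phase boundary this way: "Mono lead-in period starts with the first dose of BMS986205 and end prior to first dose of nivolumab".

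**The concern.** To show what BMS-986205 alone does to kynurenine and tryptophan, each participant needs a value before the drug and a value on the drug before nivolumab. The schedule supplies the second and not the first, and the SAP then uses the second as its zero point. What remains is the increment after C1D1 predose. That increment mixes the C1D1 dose of BMS-986205, any further accumulation, and nivolumab.

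Results produced exactly as planned would leave out whatever effect was reached during the lead-in. If inhibition has levelled off by then, the C1D2 predose summary would show almost no change, and a reader could take this as weak PD activity. No primary result and no safety decision depends on this endpoint.

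Two smaller points go with it. The bare label C1D1 in SAP 7.8 fits two of the four rows in Table 9.6-1. Also, the ECG note in Table 2-2, which applies to C0D1 and C0D14, says that ECGs "should be completed prior to any PK/PD sample blood collections when assessments occur at the same time points", although Table 9.6-1 contains no Cycle 0 PD sample.

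**Working it through.** The plan gives no figure to reproduce here. The check is a count of samples against the dosing calendar, followed by the algebra of percent change.

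**Step 1: place the samples.** First BMS-986205 dose: C0D1. First nivolumab dose: C1D1, about 30 minutes after that day's BMS-986205. Lead-in doses: nominally 14. The 75% rule gives 0.75 × 14 = 10.5, so at least 11.

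| Table 9.6-1 row | BMS-986205 already given | Nivolumab already given |
|---|---|---|
| C1D1 predose | lead-in (11 to 14 doses) | no |
| C1D1, 6 hours | lead-in plus C1D1 dose | yes |
| C1D2 predose | lead-in plus C1D1 dose | yes |
| Disease progression | variable | not fixed by schedule |

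- Samples before any BMS-986205: 0 of 4.
- Samples timed to fall on monotherapy: 1 of 4 (C1D1 predose). Under SAP 6.1 it belongs to the lead-in period, because it precedes nivolumab.
- Rows that match the label C1D1: 2 of 4.

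**Step 2: look for a substitute.** In Table 9.5.2-1 the first C0D1 BMS-986205 sample is plasma at 1 hour postdose, and the first nivolumab serum sample is C1D1 predose. No scheduled PK sample supplies pre-drug serum. The general baseline rule in SAP 6.1 (before the first dose of study treatment) would have no PD value to use.

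**Step 3: percent change under a C1D1 predose baseline.** Set the pre-drug level to 100. Let T be the fall reached by C1D1 predose and d the further fall at a later sample, both in points of the pre-drug level.

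- Change from pre-drug at the later sample: −(T + d)%.
- Change reported under SAP 7.8: −d / (100 − T), as a percentage.
- Change reported at C1D1 predose: 0, whatever T is.

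The documents give no effect sizes. T = 30, 50, 70 and the ranges of d are assumptions, shown for kynurenine.

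| T | C1D2 predose, d = 0 to 1: from pre-drug | SAP reports | C1D1 6 hours, d = 5 to 10: from pre-drug | SAP reports |
|---|---|---|---|---|
| 30 | −30 to −31% | 0 to −1.4% | −35 to −40% | −7.1 to −14.3% |
| 50 | −50 to −51% | 0 to −2.0% | −55 to −60% | −10.0 to −20.0% |
| 70 | −70 to −71% | 0 to −3.3% | −75 to −80% | −16.7 to −33.3% |

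For example, with T = 50 and d = 10 the SAP value is −10/50 = −20.0%, against −60% from pre-drug. The loss is nearly total only at C1D2 predose, and only if a plateau has been reached. The progression sample could move in either direction.

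**The case against.** The strongest reply is that the objective is partly met. The protocol endpoint is the measurement of serum levels; change from baseline enters only in the SAP. The C1D1 predose level on monotherapy is collected, and using it as a reference does not prevent its being reported. That is true, but a level on drug without a pre-drug value does not show what the drug did, and the SAP's stated endpoint is change.

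Protocol 10.3.5 says that the PD analyses will be presented separately from the main study report, so SAP 7.8 may not be the whole PD analysis. The statements above about reported values are therefore limited to the SAP 7.8 summaries. A separate report cannot supply a sample that was never drawn.

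Parts of Protocol 9.6 and of SAP 4.3 are blacked out. A hidden pre-drug sample cannot be excluded outright, but Table 9.6-1 is visible with four rows and Table 2-2 independently has no PD row.

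The ECG note may be generic wording about the order of procedures, in which case it contradicts nothing. It deserves a check, not weight. Similarly, predose is the only sensible reading of C1D1, so that point is a one-word clarification. The progression sample could fall in the lead-in, but it too would lack a pre-drug reference.

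The effect sizes are hypothetical, and tryptophan is not illustrated. The count of samples is the only magnitude that rests on the documents. Finally, the SAP dates from 2021, so an added sample may come too late; this affects which remedy applies, not whether the gap exists.

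**Conclusion.** The concern holds on the visible text. None of the four scheduled PD samples precedes BMS-986205, and the one timed to fall on monotherapy is the baseline. The change on BMS-986205 alone is not estimable for any of the 12 planned participants, and the total change from pre-drug on the combination is not estimable either. What the SAP 7.8 changes show is the increment after C1D1 predose, which cannot be attributed to nivolumab alone.

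The size of any understatement depends on how much effect the lead-in has already produced, which the documents do not say. Under the assumed 30 to 70% falls, the reported change at C1D2 predose would be between 0 and about −3%. The conclusion also assumes that the redacted text adds no Cycle 0 PD sample and that C1D1 means C1D1 predose. Because the endpoint is secondary and descriptive, this should be fixed but does not threaten the primary analysis.

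**What to change.** **For participants still to be dosed, including any expansion cohort:**

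- Add a C0D1 predose serum row to Protocol Table 9.6-1 and a PD row to Table 2-2.
- In SAP 4.3.5 and 7.8, define the PD baseline as C0D1 predose.
- Report C1D1 predose as the monotherapy time point, and C1D1 6 hours and C1D2 predose as combination time points.
- Keep the change from C1D1 predose as a secondary, incremental summary, not attributed to nivolumab alone.

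**If collection is finished:**

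- Name C1D1 predose as the reference in SAP 7.8.
- Label the results as combination-phase change after the BMS-986205 lead-in.
- State that PD activity of BMS-986205 alone cannot be estimated as a change from pre-drug.

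In either case, reconcile the Table 2-2 ECG note with Table 9.6-1.

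The cost is one extra serum tube at C0D1, when participants are already admitted before dosing and a predose methemoglobin sample is due, plus a few lines in the protocol and SAP. The SAP is dated 06-Oct-2021 and recruitment status is not stated. If sampling is over, the cost is wording only, at the price of a narrower stated objective.
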